5.2 Follow-up visits

5.2.1 D2 to D5 (all data recorded at 10 O’Clock in the morning)

- Vital status
 - Weight of the patient
 - Daily fluid balance
 - Co-infection or not
 - Specific treatment received for SARS-CoV-2 (CTC, Remdesivir)
 - Diuretics
 - RRT or not
 - Ongoing prone-positioning (prone positioning on the day on the evaluation)
 - Standard clinical monitoring (arterial pressure, heart rate)
 - Ventilatory settings:
 - VV-ECMO Y/N
 - Ventilatory mode (ACV, PSV, APRV, spontaneous breathing)
 - Tidal volume
 - Respiratory rate
 - Positive end-expiratory pressure (PEEP)
 - Plateau pressure
 - FiO₂
 - Level of catecholamines: inotrope score, calculated as IS= dose of dobutamine (µg/kg/min)+
-

- 100 x [dose of norepinephrine ($\mu\text{g}/\text{kg}/\text{min}$) + dose of epinephrine ($\mu\text{g}/\text{kg}/\text{min}$)] [16]
 - Supplementation by hydrocortisone Y/N
 - Biological exams:
 - o Arterial blood gases
 - o Haematology (blood count)
 - o Ionogram, renal and hepatic markers
 - o serum glucose, CRP, LDH, NT-pro-BNP, procalcitonin, troponin
 - o Coagulation tests: PT ratio, aPTT, fibrinogenemia, D-Dimers
 - o Albuminemia
 - ECG
 - Use of renal replacement therapy
 - SOFA score
 - Chest x-ray
 - Trans-thoracic echocardiography
- Assessment of transpulmonary thermodilution (TPT) parameters. **Two measurements will be made, one before administration of the treatment, and one 3 hours after at day 2 [7].** For day 3 to D5, one measurement will be made before administration of the treatment. **All parameters will be evaluated in supine position. Parameters recorded will be: Extra-vascular lung water index, Global end-diastolic volume index, pulmonary vascular permeability index, and cardiac index.** Central venous and arterial lines used for the routine care of the patient will be compatible with TPT systems (either PICCO, Getinge, Germany or EV1000, Edwards Lifesciences, US).
 - Treatment
 - Administration by IV perfusion (400mg FX06 intravenously or placebo as a two-time bolus within 10 minutes interval)

5.2.2 D6 to D7 (all data recorded at 10 O'Clock in the morning)

- Vital status
 - Weight of the patient
 - Daily fluid balance
 - Co-infection or not
 - Specific treatment received for SARS-CoV-2 (CTC, Remdesivir)
 - Diuretics
 - RRT or not
 - Ongoing prone-positioning (prone positioning on the day on the evaluation)
 - Standard clinical monitoring (arterial pressure, heart rate)
 - Ventilatory settings:
 - o VV-ECMO Y/N
 - o Ventilatory mode (ACV, PSV, APRV, spontaneous breathing)
 - o Tidal volume
 - o Respiratory rate
 - o Positive end-expiratory pressure (PEEP)
 - o Plateau pressure
 - o FiO_2
 - Level of catecholamines: inotrope score, calculated as $\text{IS} = \text{dose of dobutamine } (\mu\text{g}/\text{kg}/\text{min}) + 100 \times [\text{dose of norepinephrine } (\mu\text{g}/\text{kg}/\text{min}) + \text{dose of epinephrine } (\mu\text{g}/\text{kg}/\text{min})]$ [16]
 - Supplementation by hydrocortisone Y/N
 - Biological exams:
 - o Arterial blood gases
 - o Haematology (blood count)
 - o Ionogram, renal and hepatic markers
 - o serum glucose, CRP, LDH, NT-pro-BNP, procalcitonin, troponin
 - o Coagulation tests: PT ratio, aPTT, fibrinogenemia, D-Dimers
-

- Albuminemia
 - ECG
 - Use of renal replacement therapy
 - SOFA score
 - Chest x-ray
 - Trans-thoracic echocardiography at D7
 - Serum sample for immunogenicity and IL6 measurement at D7
- Assessment of transpulmonary thermodilution (TPT) parameters. **One measurement per day will be made [7]. All parameters will be evaluated in supine position. Parameters recorded will be: Extra-vascular lung water index, Global end-diastolic volume index, pulmonary vascular permeability index, and cardiac index.** Central venous and arterial lines used for the routine care of the patient will be compatible with TPT systems (either PICCO, Getinge, Germany or EV1000, Edwards Lifesciences, US).

5.2.3 D8, D10, D15

- Vital status
- Specific treatment received for SARS-CoV-2 (CTC, Remdesivir)
- Diuretics
- Ventilatory settings:
 - Ventilatory mode (ACV, PSV, APRV, spontaneous breathing)
 - Tidal volume
 - Respiratory rate
 - Positive end-expiratory pressure (PEEP)
 - Plateau pressure
 - FiO₂
- Level of catecholamines: inotrope score, calculated as IS= dose of dobutamine (µg/kg/min)+ 100 x [dose of norepinephrine (µg/kg/min) + dose of epinephrine (µg/kg/min)] [16]
- Biological exams:
 - Arterial blood gases (if clinically indicated)
- Use of renal replacement therapy
- SOFA score
- Chest x-ray (at D15 if clinically indicated)

5.2.4 Date of ICU discharge or death

- Vital status
 - Specific treatment received for SARS-CoV-2 (CTC, Remdesivir)
 - Diuretics
 - Ventilatory settings:
 - Ventilatory mode (ACV, PSV, APRV, spontaneous breathing)
 - Tidal volume
 - Respiratory rate
 - Positive end-expiratory pressure (PEEP)
 - Plateau pressure
 - FiO₂
 - Level of catecholamines: inotrope score, calculated as IS= dose of dobutamine (µg/kg/min)+ 100 x [dose of norepinephrine (µg/kg/min) + dose of epinephrine (µg/kg/min)] [16]
 - Biological exams:
 - Arterial blood gases
 - Use of renal replacement therapy
 - Chest X-ray if hospitalized and clinically indicated
 - SOFA score
 - Prescription of a highly efficient method of contraception (oral contraception associated with
-

inhibition of ovulation, intrauterine device or hormone releasing system, bilateral tubal occlusion, vasectomized partner or sexual abstinence for more than three months after inclusion), for ICU discharge of women for childbearing potential

5.3 Day 30

- Vital status
- Chest X-ray if hospitalized and clinically indicated
- Rate of withdraw or withhold life-sustaining treatments decision at Day 30
- Duration of mechanical ventilation (MV) and MV free days at D30
- Ventilator-free survival (proportion of participants alive and off invasive mechanical ventilation) at D30
- Secondary ventilator-associated pneumonia, nb of episodes
- Rescue therapy with VV-ECMO
- Catecholamine-free days at D30
- Duration of renal replacement therapy (RRT), and RRT free days at D30
- High sensitive pregnancy test

5.4 Last study visit : Day 60

An additional visit at D60 will be made by investigators by phone, asking to the medical staff in charge of the patient for the patient's status (dead, hospitalized with high-flow oxygen (more than 5 L/min), hospitalized with low-flow oxygen therapy, discharged from hospital). Serious adverse events will be also collected at this time point.

5.5 Expected length of participation and description of the chronology and duration of the study.

Length of Inclusion period 7 months

Duration of participation for each subject, of which:

- Treatment period: 5 days
- Follow-up period with treatment period: 60 days

Total study duration: 9 months

5.6 Table or diagram summarising the chronology of the study

Actions	D1	D2 to D5	D6 to D7	D8, D10, D15, ICU discharge, death	D30	D60
Information	X					
Signature of the consent form from a close relative or surrogate, or emergency consent form	X					
Randomization	X					
Administration of study drug or placebo	X	X				
Pharmacokinetic study	X					
Medical history	X					
Clinical exam	X					
Co-infection or not	X	X	X			

Weight	X	X	X			
Fluid balance		X	X			
EVLWI measured by TPT (primary endpoint)		X	X			
Standard clinical monitoring	X	X	X			
Ventilatory settings	X	X	X	X		
Doses of catecholamines	X	X	X	X		
Arterial blood gases	X	X	X	X*		
Blood pregnancy test	X				X	
NFS, TP, TCA, fibrinogen, D-Dimers	X	X	X			
Electrolytes, creatinemia, serum glucose, CRP, LDH, NT-pro-BNP, procalcitonin, troponin	X	X	X			
ECG	X	X	X			
Liver tests	X	X	X			
Albuminemia	X	X	X			
SOFA score	X	X	X	X		
RRT or not	X	X	X	X	X	
TTE	X	X	X (D7)			
Chest X-RAY	X	X	X	X*	X*	
Adverse events		X	X	X	X	
Pursuit consent		X	X	X	X	
Vital status					X	
Withhold life-sustaining treatments decision					X	
Ventilator-free survival					X	
Secondary pneumonia, nb of episodes					X	
Rescue therapy with VV-ECMO					X	
Catecholamine-free days at D30					X	
RRT free days at D30					X	
Serum sample for immunogenicity and IL6 measurement			X (D7)			
Prescription of a highly effective method of contraception for three months (for women of childbearing potential)				X (ICU discharge)		
Patient's status						X

*, if clinically indicated

5.7 Distinction between standard care and study

Procedures and treatments carried out as part of the research	Procedures and treatments associated with care	Procedures and treatments added because of the research
Treatments	Standard of care	FX-06 administration or its placebo at D1, D2, D3, D4, D5
Consultations	D1 to D30: During patient's hospitalisation's	Follow up by phone: at D30 and D60 in case of discharge from the ICU
Blood samples	Haematology - Biochemistry	Day 1 : 1 ml at time 0 (before FX06 application) and after 5, 15, 30, 60 min Day 7 : 3 ml serum
Imaging, etc.	TTE Chest X-Rays ECG	None
Monitoring	Transpulmonary thermodilution technique	

Particularly, transpulmonary thermodilution technique is part of the routine monitoring during ARDS [15].

5.8 Biological samples collection

- Pharmacokinetic study: Additional 1 ml blood sample will be taken at time 0 (before FX06 application) and after 5, 15, 30, 60 min. Because FX06 in blood is quickly degraded by endopeptidases, the following sampling procedure should be followed: 1 ml blood to be collected into tubes containing Li-heparin, mixed by inversion 10 times, and then 0.8 ml of this blood to be transferred to test tubes containing 0.08 ml of 0.88 M HCl. It is critical that blood is being transferred to acid within 2 min of collection. The tubes are closed, the acidified blood samples will be mixed by inversion 10 times, and then processed to plasma by centrifugation (2500g; 10 min). Acidified plasma samples will be stored at a temperature of less than -20°C. FX06 dosage will be processed by F4-Pharma, according to its dedicated procedure.
- An additional 3 ml serum collection will be performed at day 7, and frozen for further immunogenicity tests by the manufacturer (addendum 18.5), as well as IL6 quantification.

6 ELIGIBILITY CRITERIA

6.1 Inclusion criteria

1. Age \geq 18 years
2. SARS-CoV-2 induced pneumonia confirmed by a positive PCR test in nasopharyngeal swab or respiratory tract secretions
3. Acute respiratory distress syndrome (ARDS) according to Berlin criteria (bilateral pulmonary infiltrates on frontal chest x-ray, PaO₂/FiO₂ ratio \leq 300 mmHg, objective assessment excluding hydrostatic pulmonary oedema)
4. Need for endotracheal intubation and mechanical ventilation
5. Informed consent by patient or legal representative According to the specifications of emergency consent, randomization without the close relative or surrogate consent could be performed.
6. Affiliated to a social security system

7. Highly effective method of contraception (oral contraception associated with inhibition of ovulation, intrauterine device or hormone releasing system, bilateral tubal occlusion, vasectomized partner or sexual abstinence for more than three months before inclusion) and negative highly sensitive pregnancy test, for women of childbearing potential

6.2 Exclusion criteria

1. Mechanically ventilation for more than 4 days
2. Patient receiving drugs interfering with inflammation: non-steroidal anti-inflammatory drugs, immunoglobulins.
3. Patients receiving chemotherapy, radiotherapy or immunotherapy for malignancy
4. Participation in another interventional clinical trial
5. Women pregnant or lactating
6. Patient moribund on the day of randomization, defined by a SAPS-II score >90
7. Contra-indication for vascular access implantation for transpulmonary thermodilution monitoring
8. Severe or terminal renal insufficiency (creatinine clearance <30 ml/min)
9. Severe hepatic insufficiency (hepatic SOFA score >2)
10. Severe cardiac insufficiency, with left ventricular ejection fraction <30%
11. Any history of severe allergic drug reaction (anaphylactic shock or allergic angioedema)
12. Persons deprived of their liberty by a judicial or administrative decision (guardianship or tutelage measure)

6.3 Recruitment procedure

Recruitment will be made at admission of the patients in the 5 listed intensive care units.

	Number of subjects
Total number of subjects to be included	50
Number of sites	5
Enrolment period (months)	7
Number of subjects/site	10
Number of subjects/site/month	1.4

The recruitment will be performed gradually, stopping temporarily inclusions after each step for DSMB analysis of safety data. Each analysis will be based on a CRF extraction of mortality, mortality during the first five days, serious adverse events, clinical worsening (10.3.2.2.1, p.32) and biological tests. The following schedule will be followed for gradual interruption of inclusions:

- 10 patients (5 in each group)
- 30 patients (15 in each group)

6.4 Termination rules

6.4.1 Criteria and procedures for prematurely terminating the study treatment

As the disease may affect seriously all the organs, and regarding the short duration of the treatment, only anaphylactic reactions during administration of the drug will indicate terminating the treatment prematurely. All other adverse events will be closely monitored by the DSMB, to detect any significant imbalance between groups.

Several situations are possible

- Temporary suspension of treatment: the investigator must document the reason for suspending and resuming the treatment in the participant's source file and the case report form (CRF)

- Premature discontinuation of treatment, but the participant remains enrolled in the study until the end of their participation
- Premature discontinuation of treatment and withdrawal from the study

The investigator must:

- Document the reason(s)
- Collect the assessment criteria at the time of ending participation in the study, if the participant agrees
- Schedule a follow-up for the participant, particularly in case of a serious adverse event.

In the case of severe adverse events, the investigator must notify the sponsor and follow up the participant for 3 months following the premature discontinuation of treatment. Notification of a serious adverse event must be sent by email ([contact]) to the sponsor. The serious adverse event will be monitored until it is resolved.

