6.4.2 Criteria and procedure for premature withdrawal of a participant from the study

- Subjects may exit the study at any time and for any reason.
- The investigator can temporarily or permanently withdraw a subject from the study for any safety reason or if it is in the subject's best interests.
- Subject lost to follow-up: the subject cannot be located. The investigator must make every effort to reconnect with the subject (and record his attempts in the source file), at least to determine whether the subject is alive or dead

If a subject exits the trial prematurely or withdraws consent, any data collected prior to the date of premature exit may still be used.

The case report form must list the various reasons why the subject exited or was withdrawn from the study:

- Lack of efficacy
- Adverse reaction
- Other medical problem
- Subject's personal reasons
- Explicit withdrawal of consent
- Lost to follow-up
- Death

- ***Treatment stopping rules:***

Each investigator is strongly encouraged to stop administration of the product before the end of the treatment if any of the following events occurs, in the **absence of a clear underlying cause other than treatment administration:**

- Serious bleeding event (necessitating the transfusion of more than 4 packed red cells) in the absence of any invasive procedure.
- Severe diffuse intravascular coagulation, with QT a ratio <20%
- Severe liver cytolysis, with AST and ALT above 10 times normal
- Severe leucopenia (<500 G/L)
- Severe allergic reaction (anaphylactic shock, angio-edema, bronchospasm, severe skin reaction) at the time of or following drug injection
- Severe cardiac arrhythmia at the time of drug injection

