Crystalloids will be allowed in case of circulatory failure with signs of pre-load dependence. The solution used will be NaCl 0.9%, and ringer lactate encouraged after 2 liters.

- Packed red cells will be allowed if Hb<7g/dl or active bleeding. Fresh frozen plasma if thromboplastin time ratio<20% or if severe bleeding.
- Platelets will be allowed if <30 G/L or in case of severe bleeding.
- Albumin will not be allowed, as its efficacy is not demonstrated in this pathology, and neither in a large randomized trial in SIRS associated with sepsis [17].
- Adjunctive hydrocortisone and fludrocortisone will be discouraged, as its efficacy has not been demonstrated to date in this pathology.

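### Section 6.4.1 allows study drug to be stopped only for anaphylaxis, section 6.4.2 lists six reasons to stop, and two of the limits in that list are miswritten

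*Protocol*

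**What the plan says.** Protocol section 6.4.1, which governs early termination of study treatment, reasons that the disease can affect every organ and that treatment is short. It concludes that "only anaphylactic reactions during administration of the drug will indicate terminating the treatment prematurely". It continues: "All other adverse events will be closely monitored by the DSMB, to detect any significant imbalance between groups".

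Section 6.4.2 is headed as the section on withdrawal from the study, but it contains a block of treatment stopping rules. This begins "Each investigator is strongly encouraged to stop administration of the product before the end of the treatment if any of the following events occurs", on condition that there is an "absence of a clear underlying cause other than treatment administration". Six events follow:

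- serious bleeding (more than 4 packed red cells, no invasive procedure);
- a coagulation item, written as "Severe diffuse intravascular coagulation, with QT a ratio <20" per cent;
- liver cytolysis, defined by both transaminases exceeding tenfold normal;
- a white-cell item, written as "Severe leucopenia (<500 G/L");
- an allergic item, written as "Severe allergic reaction (anaphylactic shock, angio-edema, bronchospasm, severe skin reaction) at the time of or following drug injection";
- a cardiac item, for serious rhythm disturbance when the drug is injected.

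Section 7.4 bears on the two laboratory limits. It allows platelets below 30 G/L, and it says "Fresh frozen plasma if thromboplastin time ratio<20% or if severe bleeding". The coagulation tests in sections 5.1, 5.2.1 and 5.2.2 are PT ratio, aPTT, fibrinogen and D-dimers.

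**The concern.** The two sections give different answers to one bedside question: should this patient receive the next dose? A reader who looks under the heading on stopping treatment finds the narrow rule. The longer list sits under the heading on leaving the study. An investigator who sees unexplained severe liver cytolysis on day 3 may continue under 6.4.1 or stop under 6.4.2, and either action follows the protocol.

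DSMB review does not replace a rule for the individual patient. Treatment lasts 5 days (section 5.5). The planned recruitment pauses come after 10 and 30 patients (section 6.3), and 6.4.1 has the DSMB look for imbalance between groups. Section 10.3.2.2.2 also treats liver cytolysis, intravascular coagulation, leucopenia and rhythm disorders as natural course of the condition, exempt from notification without delay. For these events the investigator's stopping rule carries most of the weight. Section 10.1 singles out coagulation as a theoretical drug effect, yet the coagulation limit is one of the two that cannot be applied as written.

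At stake are consistent safety handling and consistent exposure to FX06 across the ICUs of a 50-patient trial.

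**Working it through.** **1. The two rules side by side**

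| Event in 6.4.2 | Permitted as a reason to stop by 6.4.1? |
|---|---|
| Serious bleeding | No |
| Intravascular coagulation | No |
| Liver cytolysis | No |
| Leucopenia | No |
| Severe allergic reaction | In part: 6.4.1 covers only anaphylaxis during administration; 6.4.2 adds angio-edema, bronchospasm, severe skin reaction and the time after injection |
| Severe arrhythmia at injection | No |

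Count: 6 listed, 1 allergic, 6 − 1 = 5 wholly outside 6.4.1. The remaining one is only partly inside it.

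**2. Can the wording be reconciled?** Section 6.4.1 uses an exclusive term and makes no exception for events suspected to be due to the drug. The condition in 6.4.2 (no other clear cause) therefore does not remove the overlap. Neither section cites the other.

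**3. The leucopenia limit**

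- Meaning of the unit: a platelet limit of 30 G/L (section 7.4) makes sense only if 1 G/L = 10^9/L. Since 1 L = 10^6 microlitres, 1 G/L = 1,000 per microlitre, and 30 G/L = 30,000 per microlitre.
- The limit as written: 500 G/L = 500 × 1,000 = 500,000 per microlitre. Practically every patient is below this.
- If 500 per microlitre was intended (an assumption): 500 / 1,000 = 0.5 G/L.
- Ratio of written to assumed limit: 500 / 0.5 = 1,000.

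**4. The coagulation limit.** The test named in 6.4.2 appears nowhere in the visit schedule. Section 7.4 applies the same 20% figure to the thromboplastin time ratio when deciding on plasma, and the PT ratio is collected daily from D1 to D7. The PT ratio is therefore the probable intention. This is an inference; the number itself is not shown to be wrong.

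**The case against.** The best defence is that the sections address different situations. On that reading 6.4.1 concerns organ events attributable to the disease and gives the only mandatory reason to stop, while 6.4.2 is advice for events suspected to come from the drug. Section 6.4.1 itself provides for temporary suspension and early discontinuation with documented reasons, and 6.4.2 lets the investigator withdraw a patient for any safety reason. Section 10.3.2.2.1 requires major bleeding without an invasive procedure, and anaphylactic shock at injection, to be reported within 24 hours. The two limits look like slips: an intensivist would not apply a severe leucopenia rule to a normal count, and a PDF-reading fault cannot be excluded for the coagulation term.

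Part of this stands. Patients are not left unprotected. Because 6.4.2 is advisory and rests on a causality judgement, some variation between investigators would remain even if 6.4.1 were corrected. Patients who exit are still analysed by randomised group (section 6.4.4), so no directional bias in the primary comparison follows.

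The split between mandatory and advisory is not in the text, however, and the exclusive wording of 6.4.1 contradicts it. A reading fault would not readily explain 500 G/L, and a safety threshold should not depend on the reader correcting it.

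**Conclusion.** The concern holds. The protocol contains two incompatible rules for stopping study drug: five of the six events in 6.4.2 fall outside the only reason that 6.4.1 permits, and the sixth is wider in type and timing. The leucopenia limit is wrong as written, on the protocol's own use of G/L; the factor of 1,000 rests on the assumption that 500 per microlitre was meant. The coagulation limit cannot be applied as written, and reading it as PT ratio below 20% needs the sponsor's confirmation.

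The consequence is inconsistent safety handling and drug exposure, not a demonstrated bias in the primary analysis. The number of patients affected cannot be computed from the protocol. This should be corrected.

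**What to change.** - In 6.4.1, replace the sentence that limits stopping to anaphylaxis with a single list of stopping events, and say whether the list is binding or advisory. In 6.4.2, delete the separate list and refer to 6.4.1.
- Write the limits as leucocytes <0.5 G/L and PT ratio <20%, both to be confirmed by the sponsor.
- Use the same list wherever the eCRF records discontinuation of treatment.
- Leave the choice of events on the list to the clinical team and the DSMB.

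The cost is a protocol clarification. No extra data are needed: blood count, PT ratio and liver tests are already scheduled daily from D1 to D7 (sections 5.1, 5.2.1, 5.2.2 and 5.6).
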